10.2 Analysis of Secondary Outcomes

For analysis of the 6 month CPSS time point, which will assess persistence of the treatment effect between the CBT and usual care groups, we will use restricted maximum likelihood estimation⁴ under a generalized linear mixed model. We will again adjust for the same variables as described above for the main efficacy analysis, except that time will be coded as binary (10 weeks vs 6 months). The primary efficacy evaluation will be performed using an interaction between the CBT versus usual care group indicator and time. We will adjust for 1 month baseline CPSS in this analysis.

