4.3 Method of Treatment Assignment and Randomization

Randomization of children eligible after the second screen was conducted using permuted blocks with equal allocation to each arm stratified by center (UU, UT, CI) and age group (8-11yrs, 12-16yrs). The randomization protocol was developed by the statistical team and implemented via REDCap.

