5. SAMPLE SIZE DETERMINATION

Goal enrollment is 53 children per group (106 total). This will provide 80% power

at a 0.05 significance to detect an effect size of 0.5.

The following table indicates sample sizes per group and total sample size for our 2 arm study under different combinations of correlation and effect size. With a correlation between baseline and follow-up CPSS measurements of 0.55, and an expected large effect size of 0.5, we would have 80% power at a 0.05 significance level to detect this difference with 45 subjects per group (90 total). Expecting a loss-to-follow-up (LTF) rate of 15%, we would need to enroll 53 subjects/group or 106 total. These calculations are based on an ANCOVA model, and were conducted in PASS v 16.0.6.

correlations and effect sizes.						
					Sample Siz	e
			Sample Si	ze	Adjusted for	or LTF
	Effect	Adjusted				
Correlation	Size	SD	N/Group	Total N	N/Group	Total N
None	0.35	1.00	130	260	153	306
0.4	0.35	0.92	110	220	129	258
0.55	0.35	0.84	90	180	106	212
None	0.50	1.00	64	128	75	150
0.4	0.50	0.92	53	106	62	124
0.55	0.50	0.84	45	90	53	106

Table 3. Sample size calculations for different combinations of within subject correlations and effect sizes.

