We plan to include all CPSS post therapy follow-up measures, regardless of timing. At the time of writing (3/31/23) we have 4 subjects prior to 10 weeks (59-65 days) in the CBT arm (none in usual care) and 8 subjects after (78-96 days) in the CBT arm and 1 subject after (105 days) in the control arm due to an issue with REDCap programming that sent the post-therapy assessment at the finish of therapy instead of 10 weeks. The REDCap issue was corrected. Since more subjects come after the window in the CBT arm this introduces an anticonservative bias. We will handle this in two ways: adjusting for time since randomization as a continuous variable in our analysis (primary strategy) and dropping these kids from our analysis (secondary strategy). The downside to our primary strategy is that it assumes that recovery is consistent over time. In reality, it's likely that more recovery happens earlier, so that this would be a conservative approach (but if more recovery happened later, then this would potentially be anticonservative). Another downside is that reviewers will have a difficult time understanding our rationale – but it is defensible and potentially takes an

anticonservative bias and makes it conservative. The downside to the secondary strategy is a loss of power.

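### The mixed model in SAP Section 10.2 omits the timing correction that Section 7.2 calls for, so its 10-week contrast and its group-by-time interaction carry a small uncorrected bias

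*Combined protocol and SAP*

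**What the plan says.** Section 7.2 reports that a REDCap programming error sent the post-therapy assessment when therapy ended rather than at 10 weeks. As of 3/31/23, the CBT arm had 4 scores taken early (days 59 to 65) and 8 taken late (days 78 to 96). Usual care had none early and 1 late (day 105). The SAP draws its own conclusion: "Since more subjects come after the window in the CBT arm this introduces an anticonservative bias". It then names two remedies, "adjusting for time since randomization as a continuous variable in our analysis (primary strategy") and, as the secondary strategy, dropping the affected children. Neither is restricted to one model.

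Section 10.1 puts continuous time since randomization into the 10-week model. It also gives timing sensitivity analyses, for that model only.

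Section 10.2 analyses 10-week and 6-month CPSS together in a mixed model. It keeps the primary model's covariates, "except that time will be coded as binary (10 weeks vs 6 months"), and makes the group-by-time interaction the efficacy evaluation. It contains no term for timing within a visit and no timing sensitivity analysis.

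**The concern.** The only time variable among the primary model's covariates is time since randomization. The natural reading of Section 10.2 is therefore that the visit code replaces it. Scores taken on day 59 and on day 105 both become 10-week scores, and the adjustment that Section 7.2 considers necessary is lost.

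With two visits, the interaction is the 6-month effect minus the 10-week effect. An error in the 10-week effect enters it in full, with the sign reversed. On the SAP's own reasoning the uncorrected 10-week effect flatters CBT, so an effect that persists would tend to look as though it fades.

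Section 10.3 applies similar approaches to the child and parent CPSS scores and the other exploratory outcomes, and repeats the secondary analysis in children scoring 15 or more. Those analyses inherit the gap.

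**Working it through.** **1. The plan's sample size, which supplies the number per arm.** Section 5 plans "at a 0.05 significance to detect an effect size of 0.5", at 80% power. It continues: "With a correlation between baseline and follow-up CPSS measurements of 0.55", for which its table gives an adjusted SD of 0.84 (√(1 − 0.55²) = 0.835). Allocation is 1:1 (Section 4.3). Taking the test as two-sided, which the SAP does not state:

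n per arm = 2 × (1.960 + 0.842)² × (0.84/0.5)² = 44.3, rounded up to 45.

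This agrees with the planned 45 per group. Allowing for 15% loss, 45/0.85 = 52.9, so 53 per arm and 106 in total, as stated. The figures reproduce. The textual point does not depend on them; 45 is used only to average the timing imbalance.

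**2. Imbalance in assessment day.** Inputs are the Section 7.2 counts and day ranges. Assumptions are 45 scored per arm and every other score at day 70. The difference in mean day (CBT minus usual care) is

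[sum of CBT deviations from day 70 − (105 − 70)] / 45.

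- At the interval midpoints (late 87, early 62): (8×17 − 4×8 − 35)/45 = 69/45 = 1.5 days.
- Latest feasible placement: (7×26 + 8 − 3×5 − 11 − 35)/45 = 129/45 = 2.9 days.
- Earliest feasible placement: (7×8 + 26 − 3×11 − 5 − 35)/45 = 9/45 = 0.2 days.

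The last two lines respect the stated ranges, which require at least one child at each end. CBT is later under every placement, even after counting the four early CBT scores and the day-105 usual-care score. With 53 per arm the figures are 1.3 days (0.2 to 2.4).

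**3. Shift in the contrast.** Shift = difference in days × recovery slope. The documents give no slope; 0.005 to 0.02 SD per day is assumed.

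- Midpoint: 1.53 × 0.005 = 0.008 SD, and 1.53 × 0.02 = 0.031 SD.
- Upper feasible limit: 2.87 × 0.02 = 0.057 SD.

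**4. Check by simulation.** There were 4,000 runs per slope, with 45 per arm, complete data, all pairwise correlations 0.55, and a true effect of −0.5 SD at both visits (true interaction zero). Mistimed days were spread evenly over the stated ranges. The models held treatment, baseline and timing, without site or age group. Means of the estimates, in SD:

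| Slope (SD/week) | 10-week effect, continuous time | 10-week effect, binary-time mixed model | 6-month effect, mixed model | Interaction, no timing term | Interaction, with days from day 70 |
|---|---|---|---|---|---|
| 0 | −0.501 | −0.501 | −0.501 | 0.000 | 0.000 |
| 0.05 | −0.493 | −0.503 | −0.498 | 0.005 | −0.006 |
| 0.10 | −0.498 | −0.520 | −0.495 | 0.024 | 0.002 |
| 0.20 | −0.499 | −0.544 | −0.503 | 0.041 | −0.003 |

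The Monte Carlo error of each mean is about 0.2/√4,000 = 0.003. Within the same runs, omitting the timing term moves the interaction by 0.011, 0.022 and 0.044 SD at the three non-zero slopes. The arithmetic of step 3 at those slopes gives the same values. The mixed model's 10-week effect matches, on average, the primary model without time (−0.504, −0.520, −0.544), which is the estimate Section 7.2 regards as biased.

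**The case against.** **The size is trivial.** The simulated SD of the interaction estimate is about 0.2. A shift of 0.01 to 0.03 SD is 5% to 15% of one standard error, and at 0.03 SD a nominal 5% test becomes about a 5.3% test. This stands, and it sets the rank of the point.

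**The 6-month endpoint is biased.** A reader might infer this, because Section 3.2.2 defines the secondary outcome as CPSS at 6 months. The documents do not support it. In the simulation the 6-month contrast stayed between −0.495 and −0.503 against a true −0.5. Only the 10-week contrast and the interaction move.

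**6-month scores are mistimed too, or the imbalance is growing.** Neither can be inferred. Section 7.2 describes an error in the post-therapy assessment only, and says it was corrected. If later scores are on time, the counts stay fixed, and the imbalance depends on the final number analysed.

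**The paper will carry two conflicting 10-week effects.** This is weak. Section 10.2 does not say that the mixed model's 10-week effect will be reported. Section 10.1 already plans a 10-week model without time. The two estimates would also differ by chance (SD about 0.024) with no recovery slope at all.

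**Adjusting for timing is itself questionable.** Timing in the CBT arm followed the end of therapy, a post-randomization event. The slope would rest on 13 listed scores, and the simulation took timing as unrelated to prognosis. These are fair cautions, but they apply equally to the primary strategy the SAP adopted for the 10-week model. They do not explain why one model is adjusted and the other is not. Summarizing mistimed scores by arm, as Section 7.2 promises, describes the imbalance without correcting it.

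**Conclusion.** The point holds as an inconsistency between Sections 7.2 and 10.2. The bias the SAP names is addressed in the 10-week model and left in the quantity Section 10.2 evaluates. Its direction is towards apparent fading of the CBT effect, provided that children in both arms are improving at around 10 weeks. Its likely size is about 0.01 to 0.03 SD, and at most about 0.06 SD over the assumed slopes, against a planned effect of 0.5 SD. A steeper slope of 0.20 SD per week (0.029 SD per day) at the latest feasible placement would give 2.87 × 0.20/7 = 0.08 SD.

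These figures rest on the 3/31/23 counts, 45 scored per arm, all other scores at day 70, complete data and linear recovery. The final counts and the recovery slope are not in the documents. This is a minor point, worth correcting because it costs little and leaves no timing decision to be made after the data are seen.

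**What to change.** In Section 10.2, keep the binary visit term and add one continuous covariate: actual day minus 70 for 10-week scores, set to zero for 6-month scores. Then repeat the model without the mistimed 10-week scores as a sensitivity analysis. Together these carry both Section 7.2 strategies into the mixed model. Continuous time since randomization should not simply be added beside the visit code, because the two would be nearly collinear. A corresponding 6-month term is needed only if 6-month mistiming is found. State that the same rule applies to the Section 10.3 analyses that use this model.

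The cost is SAP wording and one parameter, using dates Section 10.1 already needs. The loss of precision is negligible: at 0.10 SD per week the SD of the interaction estimate was 0.200 with the term and 0.198 without. The term brings the same linear-recovery assumption that Section 7.2 already accepts.

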10.3 Analysis of Exploratory Outcomes

Similar analysis approaches will be used for the separate child and parent CPSS scores, and the other exploratory outcomes described previously. As the non-CPSS exploratory outcomes are not assessed at the 1 month time point, but they are available at 1 week after injury, we will use this 1 week time point as our baseline measure.

As an exploratory analysis, we will repeat the primary and secondary analyses within the subgroup of kids who have a CPSS score of 15+.

